#### 6.8.2. Chronic Systemic Glucocorticoid Medication

Chronic systemic glucocorticoid therapy is allowed for no more than two 14-consecutive day periods during study treatment period. Each period must be at least 30 days apart.

This restriction does not apply to glucocorticoid therapy used as replacement therapy for adrenal insufficiency, or topical, intraocular, intranasal, inhaled preparations, and intra-articular injections.

## 6.8.3. Antihyperglycemic Medications

This table shows the conditions for use of concomitant antihyperglycemic medications.

Drug Class	Use during Screening or Lead-In	Conditions for Use after Randomization			
	Y = yes, if on stable therapy 90 days prior to screening. N = No	During Treatment Period	Acute Therapy Treatment for up to 14 days	Rescue Therapy	During Safety Follow- Up Period
GLP-1 RAs	Y	Yes, if on	N/A	Y	Y
DPP-4 inhibitors	Y	stable therapy	N/A	Y	Y
SGLT2 inhibitors	Y	90 days prior to screening	N/A	Y	Y
Nonstudy basal insulins	N	N	Yes, only if study basal insulin is temporarily discontinued	See Note	Y
Insulin mixtures	N	N	Yes, only if study basal insulin is discontinued	See Note	Y
Prandial insulin	N	N	Y	Y	Y
Meglitinides	N	N	N/A	N	Y
Dual GIP/GLP-1 RAs (for example, tirzepatide)	N	N	N/A	N	Y
Alpha-glucosidase inhibitors	Y	Yes, if on stable therapy 90 days prior to screening	N/A	Y	Y
Sulfonylureas	N	N	N/A	N	Y
Thiazolidinediones	Y	Yes, if on stable therapy 90 days prior to screening	N/A	Y	Y
Metformin a	Y	Yes, if on stable therapy 90 days prior to screening	N/A	Yes, if the dose is below maximum approved dose per country-specific label	Y

Abbreviations: DPP-4 = dipeptidyl peptidase-4; GIP = glucose dependent insulinotropic peptide; GLP-1 RA = glucagon-like peptide-1 receptor agonist; N = no; N/A not applicable; SGLT2 = sodium-glucose cotransporter 2; Y = yes.

<sup>a Switching metformin manufacturer is allowed if the dosage is the same. Changing to a metformin formulation with a different action profile (that is, from short-acting to long-acting metformin) is not permitted.

Note: Participants who require a nonstudy basal insulin or insulin mixture as rescue therapy must first discontinue study intervention (LY3209590 or insulin glargine). The participant will remain in the study and follow procedures for the remaining study visits.

Dose adjustments of allowable non-insulin antihyperglycemic medications are permitted after randomization under the following circumstances:

- situations that require short-term treatment interruption consistent with the product labeling for each respective country
- situations that require dose adjustment or discontinuation per country-specific label, for example, in the case of reduced estimated glomerular filtration rate
- in the case of increased hypoglycemia risk during the treatment period (as described in Section 8.3.6)
- a dose increases as part of rescue therapy, and
- for safety reasons at the discretion of the investigator.

Any changes in dose should be documented.

## 6.9. Nonstudy Treatment after the End of the Study

The investigator will assess each participant to determine the need to transition to a nonstudy treatment for T2D at visits described in the SoA. Unscheduled visits, in addition to those described in the SoA, may occur during this time to facilitate the transition.

The participant's FBG and other clinical factors should be used to guide dose initiation and adjustment in accordance with the country-specific label.

A daily basal insulin is not required until the FBG is above 120 mg/dL for 2 consecutive measurements.

If a nonstudy daily basal insulin is required, start the dose at 10 U/day and adjust based on FBG and investigator judgment in accordance with any country-specific label.

#### Study participants treated with LY3209590

Since LY3209590 has a half-life of approximately 17 days, a careful titration of any new antihyperglycemic treatment will be necessary to prevent hypoglycemia due to overlapping action. The investigator should consider titrating the daily insulin to reach 50% of the required daily dose at approximately 2 weeks and 80% at approximately 4 weeks.

#### Study participants treated with insulin glargine

Study participants assigned to insulin glargine will transition to a nonstudy treatment after Visit 33. The investigator will prescribe the nonstudy treatment and titrate the dose based on their clinical judgment in accordance with the country-specific label.

## 7. Discontinuation of Study Intervention and Participant Discontinuation/Withdrawal

Discontinuation of specific sites or of the study as a whole are handled as part of Section 10.1.9.

## 7.1. Discontinuation of Study Intervention

When necessary, a participant may be permanently discontinued from study intervention. If so, the participant will remain in the study and follow procedures for remaining study visits, as shown in the SoA.

Participants who stop the study intervention permanently may receive another glucose-lowering medication. The new glucose-lowering medication will be recorded on the CRF for antihyperglycemic medications.

A participant should be permanently discontinued from study intervention if

- the participant becomes pregnant during the study
- the participant requests to discontinue study intervention
- the participant is receiving a 100 U dose and needs a dose reduction
- the participant is diagnosed with an active or untreated malignancy, except for successfully treated basal or squamous cell carcinoma
- the participant did not take insulin glargine for more than 21 consecutive days or missed more than 3 consecutive doses of LY3209590 at any time during the study, or
- in the opinion of the investigator, the participant should permanently discontinue the study intervention for safety reasons.

## 7.1.1. Liver Chemistry Stopping Criteria

The study intervention should be interrupted or discontinued if 1 or more of these conditions described in this table occur.

Elevation	Exception		
ALT or AST >8x ULN			
ALT or AST >5x ULN for more than 2 weeks			
ALT or AST >3x ULN and either TBL >2x ULN or INR >1.5	In participants with Gilbert's syndrome, doubling of direct bilirubin should be used for intervention interruption or discontinuation decisions rather than TBL >2x ULN.		
ALT or AST >3x ULN with the appearance of fatigue, nausea, vomiting, right upper quadrant pain or tenderness, fever, rash,			
and/or eosinophilia (>5%)			
ALP >3x ULN, when the source of increased ALP is the liver			
ALP >2.5x ULN and TBL >2x ULN	In participants with Gilbert's syndrome, doubling of direct bilirubin should be used for intervention interruption or discontinuation decisions rather than TBL >2x ULN.		
ALP >2.5x ULN with the appearance of fatigue, nausea, vomiting, right upper quadrant pain or tenderness, fever, rash, and/or eosinophilia (>5%)			

Resumption of the study intervention can be considered only in consultation with the Lilly-designated medical monitor and only if the liver test results return to baseline and if a self-limited, non-intervention etiology is identified.

## 7.1.2. Hypersensitivity Reactions

If the investigator determines that a systemic hypersensitivity reaction has occurred related to study intervention administration, the participant may be **permanently discontinued** from the study intervention, and the sponsor's designated medical monitor should be notified.

If the investigator is uncertain about whether a systemic hypersensitivity reaction has occurred and whether discontinuation of study intervention is warranted, the investigator may consult the sponsor.

#### 7.1.3. Temporary Discontinuation of Study Intervention

#### Criteria for temporary discontinuation of LY3209590 or insulin glargine

The investigator may temporarily interrupt study treatment, due to an AE, clinically significant laboratory value, hospital visits, travel, or shortage of study treatment supply.

This will be allowed for up to 21 consecutive days for insulin glargine or 3 consecutive doses for LY3209590 at any time during the study. This information should be documented by the investigator.

#### Guidance when temporary discontinuation of study intervention occurs

Every effort should be made by the investigator to maintain participants in the study and to restart study intervention promptly, as soon as it is safe to do so.

Participants will continue their study visits and follow-up according to the SoA.

Participants should resume the dose prescribed before the temporary dosing interruption at the discretion of the investigator.

## Recording temporary discontinuation of study intervention

The dates of study intervention interruption and restart must be documented in source documents and entered on the CRF.

Participant noncompliance should not be recorded as interruption of study intervention on the CRF.

## 7.2. Participant Discontinuation/Withdrawal from the Study

Discontinuation is expected to be uncommon.

A participant may withdraw from the study

- at any time at the participant's own request
- at the request of the participant's designee (for example, parents or legal guardian)
- at the discretion of the investigator for safety, behavioral, compliance, or administrative reasons
- if the participant is diagnosed with any type of diabetes mellitus other than T2D
- if enrolled in any other clinical study involving an investigational product, or enrolled in any other type of medical research judged not to be scientifically or medically compatible with this study, or
- if the participant, for any reason, requires treatment with a therapeutic agent that is prohibited by the protocol and has been demonstrated to be effective for treatment of the study indication. In this case, discontinuation from the study occurs prior to introduction of the new agent.

At the time of discontinuing from the study, if possible, the participant will complete procedures for an early discontinuation visit and post-treatment follow-up, as shown in the SoA.

If the participant has not already discontinued the study intervention, the participant will be permanently discontinued from the study intervention at the time of the decision to discontinue the study.

If the participant withdraws consent for disclosure of future information, the sponsor may retain and continue to use any data collected before such a withdrawal of consent.

If a participant withdraws from the study, the participant may request destruction of any samples taken and not tested, and the investigator must document this in the site study records.

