## 6.5.1.3. LY3209590 Dose Adjustments Based on Hypoglycemia Events

#### Guidance for participants receiving 100 U LY3209590

If a participant is receiving a 100 U LY3209590 dose and experiences hypoglycemia, the investigator will

- rule out any other contributing factors, such as increased physical activity or illness, which may cause an unusual occurrence of hypoglycemia, and
- discontinue intervention if participant meets dose reduction criteria due to hypoglycemia.

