- If study intervention is permanently discontinued, the participant will remain in the study and follow procedures for remaining study visits, as shown in the SoA in the protocol.

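### Protocol 7.2 has a participant who needs a prohibited glucose-lowering agent leave the study before it starts, which is inconsistent with 7.1 and SAP 1.2 and can cost the Week 52 HbA1c that the US estimand needs

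*Protocol*

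**What the plan says.** Protocol 7.2 gives a list of circumstances in which a participant *may* withdraw from the study. The last covers a participant who, for whatever cause, "requires treatment with a therapeutic agent that is prohibited by the protocol and has been demonstrated to be effective for treatment of the study indication". The bullet then adds: "In this case, discontinuation from the study occurs prior to introduction of the new agent". On leaving, an early discontinuation visit and post-treatment follow-up are done if possible.

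Protocol 7.1 treats permanent discontinuation of study intervention differently: "If so, the participant will remain in the study and follow procedures for remaining study visits, as shown in the SoA". It continues: "Participants who stop the study intervention permanently may receive another glucose-lowering medication". No class is excluded. SAP 1.2 repeats the retention rule: "If study intervention is permanently discontinued, the participant will remain in the study and follow procedures for remaining study visits".

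The table in Protocol 6.8.3 marks sulfonylureas, meglitinides and dual GIP/GLP-1 RAs as not allowed either in the treatment period or as rescue. Nonstudy basal insulins and insulin mixtures are not allowed in the treatment period, apart from acute use of up to 14 days while study basal insulin is stopped. For rescue, a Note applies: "Participants who require a nonstudy basal insulin or insulin mixture as rescue therapy must first discontinue study intervention". The Note then keeps that participant in the study.

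**The concern.** A site whose participant needs, say, a sulfonylurea finds two instructions. Under 7.1 the participant stops study insulin, starts the drug and keeps attending. Under the closing sentence of the 7.2 bullet the participant leaves the study first.

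The choice matters for the US primary analysis. The treatment regimen estimand (Protocol Section 3, SAP 1.1) is defined regardless of treatment discontinuation or rescue. Its analysis uses only the baseline and Visit 33 values (SAP 4.3.2), so an HbA1c taken at an early discontinuation visit does not replace the missing one. SAP 4.3.2 itself attributes missing Week 52 values to early study discontinuation. Missing values are imputed from same-arm participants who stopped study intervention but still have a Week 52 value. A participant who leaves under 7.2 is therefore both a value to be imputed and one fewer possible donor. If either arm has fewer than 8 donors, the imputation changes to return-to-baseline.

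**Working it through.** **1. The plan's own figures.** Inputs from Protocol 9.5: 670 randomized 1:1 (335 per arm), 15% dropout, 284 completers per arm, SD 1.1%, margins 0.4% and 0.3%, no true difference, 2-sided 95% CI.
- Standard error = 1.1 × √(2/284) = 0.0923.
- Power at margin 0.4: Φ(0.4/0.0923 − 1.96) = Φ(2.37) = 99.1%.
- Power at margin 0.3: Φ(0.3/0.0923 − 1.96) = Φ(1.29) = 90.1%.
- 284/0.85, rounded up, gives 335 per arm.

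These agree with the plan. The point does not challenge them.

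**2. Which agents are affected.** The rules, by agent and use:
- Sulfonylureas, meglitinides, dual GIP/GLP-1 RAs: prohibited in the treatment period and as rescue. No note keeps the participant in the study, so 7.1 and 7.2 point in opposite directions.
- Nonstudy basal insulin or insulin mixtures outside the rescue and acute allowances: prohibited in the treatment period, with the same inconsistency.
- Nonstudy basal insulin or mixtures as rescue: settled by the Note, which keeps the participant.
- GLP-1 RAs, DPP-4 inhibitors, SGLT2 inhibitors, alpha-glucosidase inhibitors, thiazolidinediones, metformin below its maximum dose and prandial insulin: allowed as rescue, so that use does not trigger the 7.2 bullet.

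The inconsistency exists in both arms.

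**3. Effect on an arm mean.** The documents do not say how many participants would leave this way. Assume k participants in one arm, each with an imputed value wrong by e = 1.0% HbA1c. The shift is k × e / 335.
- k = 1: 1/335 = 0.003 points.
- k = 10: 10/335 = 0.030 points, which is 0.0299/0.3 = 10% of the smaller margin and 0.0299/0.4 = 7.5% of the larger.

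**4. Effect on power.** Assume an extra fraction x of each arm is lost on top of 15%, so n = 335 × (0.85 − x), using complete-data power.
- x = 1%: n = 281.4; 99.1% at margin 0.4 and 89.9% at margin 0.3.
- x = 5%: n = 268.0; 98.8% and 88.4%.

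**5. Effect on the donor rule.** The threshold of 8 is 8/335 = 2.4% of an arm. If an arm would otherwise have had 8 donors (assumed), one departure takes it below the threshold; from 12 (assumed), it takes five.

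**The case against.** The best defense is that the texts can be read together. The 7.2 list says a participant *may* withdraw, and the closing sentence can be taken to fix only the order of events if withdrawal happens. Section 7.1 is the more specific rule for people off study insulin, and it lets them take another drug; on that view the drug is no longer prohibited to them and 7.2 does not reach them. Few participants will strictly require a prohibited class when so many others are available as rescue. Missing values have a prespecified imputation, a fallback, a two-way tipping-point analysis and an imputation under the noninferiority null (SAP 4.3.2 and 4.3.3.1).

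Much of this stands. It limits the size, and it rules out saying that 7.2 compels exits. It does not remove the inconsistency. Nothing in 6.8.3 lifts the prohibition once study insulin stops, and 7.2 itself allows for participants already off study intervention. Sites could reasonably handle the same case differently. The sensitivity analyses test dependence on missing values; they cannot recover them.

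Three stronger readings are tempting but not supported:
- *A one-arm bias.* At 100 U of LY3209590 the investigator must "discontinue intervention if participant meets dose reduction criteria due to hypoglycemia", whereas glargine can be reduced by 2 to 6 U. A reader might infer that 7.2 removes participants from one arm. That asymmetry comes from the stopping rule, not from 7.2, which applies to both arms. An investigator who then chooses a prohibited drug is also not the same as a participant who requires one.
- *A likely switch to return-to-baseline imputation.* A reader might compare the threshold of 8 with the 335 − 284 = 51 planned non-completers per arm. If those are study dropouts, they have no Week 52 value and cannot be donors, so the comparison says nothing.
- *Loss of everyone who needs nonstudy basal insulin.* The Note in 6.8.3 keeps those who need it as rescue.

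**Conclusion.** The concern holds in a limited form. Protocol 7.2 is inconsistent with 7.1 and SAP 1.2 for participants who need a sulfonylurea, a meglitinide, a dual GIP/GLP-1 RA, or nonstudy basal insulin or a mixture outside the allowances in 6.8.3. A site that follows the last sentence of the 7.2 bullet creates avoidable missing data for the US primary estimand and may remove an imputation donor.

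The effect is probably small: 0.003 to 0.030 points on an arm mean, resting on the assumed 1 to 10 participants in one arm and the assumed 1.0% error each. Protocol 7.2 itself expects discontinuation to be uncommon. No direction of bias can be stated, because it depends on who leaves in each arm. The change should still be made: the rule works against the plan's own estimand and is easy to correct. Confidence is medium because of the permissive opening of the list.

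**What to change.** Amend the protocol in two places.

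1. In 7.2, delete the prohibited-agent bullet, both sentences.
2. In 7.1, state that a participant who requires a prohibited agent effective for type 2 diabetes, other than acute or rescue use allowed in 6.8.3, permanently stops study intervention before the agent starts (if not already stopped), and remains in the study through Visit 33 and safety follow-up unless they withdraw consent.

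The 14-day acute allowance in 6.8.3 stays as it is.

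No new visits or procedures are needed, since 7.1 already requires the remaining scheduled visits after a permanent stop. The price is that some participants who would have left attend further visits. Their Week 52 values on the new drug enter the US analysis, as that estimand intends. If sites had read 7.2 as permissive and kept such participants on study insulin, a few more treatment discontinuations will be recorded. That truncates those participants' data for the efficacy estimand, which SAP Section 3 cuts at the last dose plus 10 days for LY3209590 or plus 1 day for glargine, or at the start of rescue if earlier.

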## 7.3. Lost to Follow up

A participant will be considered lost to follow-up if they repeatedly fail to return for scheduled visits and are unable to be contacted by the study site. Site personnel or designee are expected to make diligent attempts to contact participants who fail to return for a scheduled visit or were otherwise unable to be followed up by the site.

## 8. Study Assessments and Procedures

Study procedures and their timing are summarized in the SoA.

Immediate safety concerns should be discussed with the sponsor immediately upon occurrence or awareness to determine if the participant should continue or discontinue study intervention.

Adherence to the study design requirements, including those specified in the SoA, is essential and required for study conduct.

All screening evaluations must be completed and reviewed to confirm that potential participants meet all eligibility criteria. The investigator will maintain a screening log to record details of all participants screened and to confirm eligibility or record reasons for screening failure, as applicable.

## 8.1. Efficacy Assessments

Efficacy will be measured by

- HbA1c
- FBG
- insulin dose, and
- patient-reported outcomes questionnaires
  - o TRIM-D
  - o DTSQ-status
  - o DTSQ-change
  - o SIM-Q
  - o DID-EQ, and
  - o Basal Insulin Experience.

See Section 3 for specific efficacy endpoints.

#### 8.1.1. Glucose Monitoring

Participants **must** use only the study-provided glucometer during the study. The use of personal glucometer or continuous glucose monitoring is not permitted.

#### 8.1.1.1. Self-Monitoring of Blood Glucose (SMBG)

#### Glucometer for participant use during the study

Participants will receive a sponsor-approved glucometer and related testing supplies for use during the study.

Site personnel will train the participant on correct use of the glucometer for self-monitoring blood glucose and reporting of hypoglycemia data in the e-diary.

Participants should use the glucometer

- for the 6-point profile
- whenever hypoglycemia is experienced or suspected

• Note: If BG values are <80 mg/dL but not below <70 mg/dL (that is, defined as hypoglycemia), recommend to the participant that they monitor their BG more frequently to prevent hypoglycemia. This is particularly relevant to participants receiving LY3209590 via the autoinjector, where dose cannot be adjusted precisely to meet glycemic requirements.

- when there is awareness of increased risk related to changes in dietary intake, physical activity, or inadvertent or atypical insulin dosing
- to check for hyperglycemic events, or
- as directed by the investigator.

#### Performing a 6-point profile

Participants will receive instructions to perform SMBG 6-point profiles over a 24-hour period on 2 nonconsecutive days during the 7-day period prior to visits shown in the SoA.

The 6-point profile consists of pre-meal and 2-hour postprandial SMBG measurements for the morning, midday, and evening meals during 1 day.

Pre-meal measurements should be taken before the participant begins eating the meal.

#### When to measure fasting blood glucose (FBG) during the study

Site personnel will train the participant to measure FBG daily when possible, and a minimum of 3 times per week using the study-provided glucometer.

Participants should not eat or drink anything but water for a minimum of 8 hours before measuring their FBG.

Participants should measure FBG upon waking in the morning after fasting overnight.

#### Glucometer data transfer

The study-provided glucometer will wirelessly transmit blood glucose measurements to the participant's e-diary. Site personnel will be able to view SMBG data that have been transmitted to the e-diary through a web-based portal as well as any reported events of hypoglycemia.

